### **C. Clinical Laboratory Results**

Laboratory test results (including serum chemistry, hematology, urinalysis, lipid panel, bone monitoring, liver function testing and thyroid panel [Module 2 only]) and abnormal laboratory values will be presented in data listings. CTCAE version 5.0 lab grades will also be presented where applicable. CTCAE grades will be derived based on laboratory results and will not factor in clinical evaluations. Grade 0 will be assigned for all non-missing values not graded as 1 or higher. For laboratory tests where grades are not defined by CTCAE version 5.0 results will be classified as low, normal, or high based on laboratory normal ranges.

Overlay line plot of observed values of lab data (including serum chemistry, hematology, urinalysis, lipid panel, bone monitoring, liver function testing and thyroid panel [Module 2 only]) will be presented for all subjects and by study module. Hys law eDISH plot will also be presented.

Shift tables will be used to summarize the changes from baseline in severity of lab CTCAE grades for will be provided for serum chemistry, hematology, and urinalysis parameters by module, dose cohorts and visit, starting from the first post-baseline visit. The shift from baseline to worst low lab grades and to worst high lab grades will be summarized by module and dose cohorts. Clinical evaluations (normal, abnormal not clinically significant, and abnormal, clinically significant) will be summarized using frequency counts and percentages for each visit as applicable. For numeric laboratory test results, summaries of actual values, changes from baseline, and percent change from baseline will also be summarized using continuous descriptive statistics at each visit.

By-patient listing will be provided by visit, including changes from baseline, grade and reference range. All values outside the reference ranges will also be flagged in the data listings. The abnormal values will be flagged with 'L' for values below the lower limit of the clinical reference range and 'H' for values above the upper limit of the clinical reference range.

Results from pregnancy tests and HIV status will be provided in data listings.

#### **D. Vital Signs**

Actual values and change from baseline of vital signs data (weight, temperature, pulse, respiratory rate, systolic blood pressure, and diastolic blood pressure) will be summarized using descriptive statistics at each visit. A listing of the vital signs data will also be provided.

#### **E. Physical Examination**

A full physical examination is assessed at screening and prior to Day 1 of each cycle. Abnormal physical examination findings will be presented in data listings.

#### **F. Electrocardiogram (ECG)**

Actual values and change from baseline of ECG parameters (PR interval, RR interval, QRS duration, QT interval, QTcB, QTcF) will be summarized descriptively by module, dose cohorts and timepoints. Note that ECGs are collected in triplicate and analyses of numeric results will be based on the average of the triplicate results.

All ECG results along with the overall evaluation [i.e., Normal, Abnormal, Not Clinically Significant, and Abnormal, Clinically Significant] will be presented in data listings.

QTcF interval absolute values will also be tabulated by the following groups:

- $\leq 450$
- $>450 - \leq 480$  msec
- $>480 - \leq 500$  msec
- $>500$  msec

Change from baseline in QTcF interval will be classified as:

- $\leq 30$  msec increase from baseline
- $>30 - \leq 60$  msec increase from baseline
- $>60$  msec increase from baseline

Frequency and percentage of QTcF categorical analysis will be summarized by module and dose cohorts. A shift table of baseline QTcF to worst on-treatment results will be presented. For rating the worst on-treatment value, the following categories will be used based on the varying degrees of abnormality above, in the order of least to most severe (top to bottom):

- Missing result
- $\leq 450$  msec (i.e. 'normal')
- $>450 - \leq 480$  msec
- $>480 - \leq 500$  msec
- $>500$  msec

#### **G. Prior and Concomitant Medications**

Prior medications are defined as medications with a stop date prior to the first dose of any study treatment. Concomitant medications are defined as medications ongoing or with stop dates on or after the first dose of any study treatment. Prior and concomitant medications will be coded using WHO Drug version March 2021, B3 Format.

To distinguish prior vs. concomitant medications, the following rules for stop dates will apply:

- If only year is recorded, and it is before Day 1, it is a prior medication; if year is same or after Day 1, it is assumed to be a concomitant medication.
- If day is missing, but month and year are before Day 1, it is a prior medication; if month and year are the same as Day 1, it is assumed to be a concomitant medication; if month and year are after Day 1, it is a concomitant medication.
- If start date is after Day 1, it is a concomitant medication regardless.

Concomitant medications will be summarized by module, dose cohort, WHO-DD ATC classification, and PT.

All prior and concomitant medications will be displayed in data listings as well.

#### **H. Prior and Concomitant Procedures**

Prior procedures are defined as procedures with a procedure date that is prior to the first dose of any study treatment. Concomitant procedures are defined as procedures with a procedure date on or after the first dose of any study treatment.

Prior and concomitant procedures will be coded using MedDRA version 24.1. Concomitant procedures will be summarized by SOC and PT by dose cohort for each module separately.

All prior and concomitant procedures will be displayed in data listings as well.

#### **I. Eastern Cooperative Oncology Group Performance Status (ECOG PS)**

A shift table of ECOG performance status from baseline to worst on-treatment value will be provided by dose cohort for each module separately.

A listing of ECOG performance status results will also be generated.

#### **J. Post Treatment Anti-Cancer Therapy**

Post treatment Anti-Cancer therapy data will be summarized by ATC and PT in the summary table and presented in the data listing.

#### **K. $\beta$ -CTX**

Absolute and change from baseline of  $\beta$ -CTX will be summarized and listed by

dose level and study module.  $\beta$ -CTX results below the lower limit of

quantification will be imputed as 0 in descriptive summaries. Subjects who received denosumab will be summarized and flagged in the listings and if clear distinction between cohorts will be noted as a footnote in the summary table.

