The DCR (SD + PR + CR) reported was 41% (13/32), which included 12 patients who achieved SD and one (TNBC) who achieved a PR. Of patients who received prior anti-PD1, 47% achieved SD (9/19). The majority of these patients were refractory to prior anti-PD1 treatment (17/19). All five patients with uveal melanoma achieved durable SD of > 24 weeks duration.

The study is ongoing with further recruitment of uveal melanoma patients planned in addition to evaluating whether AXIN2 mRNA levels may be predictive of clinical benefit.

Phase 1a safety data from an ongoing FTIM clinical study of the small molecule PORCN inhibitor ETC-159 (NCT02521844), were presented in a poster at the ASCO 2017 annual meeting {Ng, 2017 #10270}. Twenty advanced solid tumour patients were treated in the dose-escalation phase (1–40 mg ETC-159, QOD in a 28-day cycle). Two DLTs were reported (hyperbilirubinemia at 16 mg and a skeletal fragility fracture at 30 mg) and the most common AEs (irrespective of causality) were anorexia (30%), fatigue (30%), vomiting (30%), dysgeusia (30%), increased  $\beta$ -CTX (30%), nausea (20%) and constipation (20%). In the 30 mg cohort, two of five patients experienced bone-fragility fractures (one of these was classed as a DLT while the other was outside the DLT period) and four out of five patients experienced a doubling from baseline and increase to >1000 pg/mL in serum  $\beta$ -CTX levels. These patients with increased  $\beta$ -CTX (defined as a doubling from baseline to a level above 1000 pg/mL) were given bone protective treatments (denosumab or bisphosphonate), which normalised  $\beta$ -CTX levels. The MTD was therefore declared at 30 mg. Efficacy analysis in the first twenty patients showed that five had SD.

CGX1321 (Curegenix Inc) is a porcupine inhibitor in Phase 1 development in Asia as monotherapy in advanced solid tumours and in Phase 1b in combination with pembrolizumab in patients with advanced GI tumours (CRC, gastric, pancreatic, bile duct, hepatocellular, oesophageal and GI cancers). No clinical data have been reported to date on CGX1321.

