#### **3.4.1.4 Intervention Measures for Patients with Increased Bone-Fracture Risk on RXC004 Treatment**

The interventions detailed in Table 2 should be followed for all patients on RXC004 study treatment, in the event of increased bone fracture risk.

Patients with a DEXA scan showing  $\geq 7\%$  worsening in BMD at lumbar spine or total hip compared to baseline will permanently discontinue study treatment. The change in BMD that can be confidently detected is termed the least significant change (LSC). A 7% decrease in BMD is approximately the 99% confidence limit for LSC and is considered as an indicator of failure to respond to treatment. {Diez-Perez, 2012 Ref 7}.

Prophylactic denosumab (XGEVATM - 120 mg s.c. QM per approved label for prevention of skeletal-related events (SREs) in patients with bone metastases) will be administered to all patients (from the 1.5mg RXC004 monotherapy Module 1, Cohort 3). This denosumab dose and schedule is being adopted to maximise bone safety. Patients with advanced/metastatic malignancies are at potential increased risk of bone fragility if treated with a porcupine inhibitor such as RXC004. In addition, while patients with bone metastases are excluded from the protocol currently it is the intention (based on safety data and appropriate expert and regulatory review and approval) to administer RXC004 to patients with bone metastases as part of the RXC004 development programme as a significant minority of patients with metastatic disease will have bone metastases). The XGEVATM approved dose and schedule of denosumab will be used in all patients both to maximize bone safety and allow a uniform and accurate assessment of denosumab use in combination with RXC004. Denosumab, as it is a more potent inhibitor of bone resorption compared to bisphosphonates, leads to greater increases in bone mineral density. {Miller, 2016 Ref 28}

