Prophylactic use of denosumab was not adopted from start of study treatment as the significantly lower starting dose of RXC004 0.5mg (previously this was 10 mg) and the other bone protection measures reduced the potential for bone toxicity. However, as a significant number of patients (3 of 6) required denosumab treatment by the end of Cycle 1 based on reaching protocol-defined increases in  $\beta$ -CTX levels indicative of increasing risk of bone fragility, prophylactic denosumab is now administered to all patients (from the 1.5 mg RXC004 monotherapy cohort) based on a review of the data and advice by an independent expert in bone metabolism.

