### **K. Data Display Characteristics**

Data displays produced for this study will include three types—summary tables, data listings, and figures. Unless stated otherwise, data listings will be produced for all recorded data. Summary tables will be produced as specified in the following sections. Additional data listings will be produced for outcome measures that involve extensive procedures to derive the analyzed outcomes. Figures will be produced when specified in sections to follow.

Data listings will simply list the data recorded on the eCRF or derived for each patient. They will be ordered by module, dose cohort, site, patient number, and date/time of assessment. When expedient, additional levels of ordering hierarchy may reflect subsets of assessments within patient. Data listings will not display patient initials.

Summary tables will display summary statistics calculated for each module and dose cohort, as well as overall within each module, unless described otherwise in following sections.

Unless stated otherwise in relevant sections to follow, continuous data will be summarized descriptively with the number of non-missing values, mean, standard deviation, minimum, median, and maximum. Categorical data will be summarized using frequency counts and percentages.

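### In Module 1 the beta-CTX tables by RXC004 dose cannot separate RXC004 from denosumab across the 1 mg to 1.5 mg step, so a bone dose effect can look absent or inverse

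*SAP*

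**What the plan says.** **Tabulation.** SAP IX.K summarises absolute and change-from-baseline beta-CTX by "dose level and study module". The default layout in SAP VI.K adds a pooled column: "Summary tables will display summary statistics calculated for each module and dose cohort, as well as overall within each module". SAP IX.C counts bone monitoring among the laboratory tests and plans that, for numeric results, "changes from baseline, and percent change from baseline will also be summarized using continuous descriptive statistics at each visit".

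**Denosumab in the SAP.** The only provision is in IX.K: "Subjects who received denosumab will be summarized and flagged in the listings and if clear distinction between cohorts will be noted as a footnote". That note would sit under the beta-CTX table.

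**Denosumab in the trial.** Protocol 3.4.1.4 states: "Prophylactic use of denosumab was not adopted from start of study treatment". Under Protocol 3.4.1 it was introduced when beta-CTX rose by at least 350 pg/mL from baseline or went above 1,000 pg/mL. The policy then changed, "as a significant number of patients (3 of 6) required denosumab treatment by the end of Cycle 1", and prophylaxis "will be administered to all patients (from the 1.5mg RXC004 monotherapy Module 1, Cohort 3").

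**Effect of such treatment.** For another porcupine inhibitor, Protocol 1.2.5 reports that patients with raised beta-CTX "were given bone protective treatments (denosumab or bisphosphonate), which normalised" their levels. Protocol 1.7.1 reports that in this trial, since universal prophylaxis began, beta-CTX has stayed at or below baseline.

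**The concern.** The dose columns of the Module 1 table differ in two things at once: the RXC004 dose and the way denosumab was used. At 0.5 and 1 mg, denosumab was started in individual patients because the tabulated outcome had risen. Those columns therefore begin as values without denosumab and later mix unrescued patients with rescued ones, and the rescued are the patients with the largest rises. From 1.5 mg upward, prophylaxis was given to everyone.

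Bone toxicity is an on-target risk, and the primary objective is safety, tolerability and the choice of dose and schedule. Change in bone mineral density goes to listings only (SAP IX.L), so beta-CTX is the main bone measure in summary tables. Rises at the lowest doses and none above them would invite the reading that RXC004 has no dose effect on bone, or an inverse one.

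**Working it through.** The plan states no figure for this point, so there is none to reproduce. The inputs are the cohort counts (Protocol 5.4.3), the rescue count (3.4.1.4), the trigger (3.4.1) and the reported levels under prophylaxis (1.7.1).

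**1. Who had which regime (Module 1)**

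| Dose | 0.5 mg | 1 mg | 1.5 mg | 2 mg | 3 mg | 10 mg |
|---|---|---|---|---|---|---|
| Patients | 4 | 3 | 7 | 6 | 4 | 1 |

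- Total: 4+3+7+6+4+1 = 25. At 2 mg or below: 4+3+7+6 = 20. Both match the protocol.
- Rescue only: 4+3 = 7. Prophylaxis: 7+6+4 = 17, or 68% of 25.
- The denosumab status of the 10 mg patient is not in the text available.

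**2. Rescue frequency**

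3/6 = 50% (exact 95% CI 11.8% to 88.2%). The protocol does not say which six are meant and lists seven patients at 0.5–1 mg. With seven, 3/7 = 42.9% (9.9% to 81.6%).

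**3. Mean change at 0.5–1 mg**

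Let the three triggered patients have risen by R, and let the other three average m (assumed). Before rescue the mean is (3R + 3m)/6. After rescue, with the rescued back at baseline, it is (3×0 + 3m)/6.

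| m (pg/mL) | Before, R = 350 | Before, R = 100 (1,000 pg/mL level reached) | After rescue |
|---|---|---|---|
| −100 | +125 | 0 | −50 |
| 0 | +175 | +50 | 0 |
| +100 | +225 | +100 | +50 |

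Against this, 1.5–3 mg shows 0 or less if the at-or-below-baseline statement holds for each patient. With R = 350 the low-dose mean stays above zero unless the other three fell by 350 pg/mL or more on average. After rescue the contrast shrinks or disappears.

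**4. Separate columns**

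The table shows 0.5 mg (n = 4) and 1 mg (n = 3) apart, and the split of the three triggered patients is not given. Take seven patients, R = 350, m = 0, and k triggered at 0.5 mg. The means are 350k/4 at 0.5 mg and 350(3−k)/3 at 1 mg. For k = 0, 1, 2, 3 the pairs are (0, 350), (87.5, 233.3), (175, 116.7) and (262.5, 0). The higher column is at least +175 in every case. This assumes that all three triggered at the same visit.

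**5. Can a rising dose-response look like a fall?**

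A simulation used assumed values: baseline median 400 pg/mL (log-scale SD 0.4, capped at 1,000), untreated change 150 + 200 × dose with SD 150, and denosumab placing values 0 to 60% below baseline.

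| Dose | True untreated change | Table before rescue | Table after rescue or under prophylaxis |
|---|---|---|---|
| 0.5 mg | about +250 | about +250 | +44 to +130 |
| 1 mg | about +350 | about +350 | −37 to +108 |
| 1.5, 2, 3 mg | about +450, +550, +750 | – | 0 to −258 at each dose |

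The flat result from 1.5 mg is built into the assumption that denosumab overrides RXC004. The simulation shows what can happen, not what did.

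**The case against.** **The SAP already sees the problem.** Its footnote condition is met between the cohorts up to 1 mg and those from 1.5 mg, and recipients are to be summarised as well as flagged. That stands as a partial safeguard. But the SAP does not define what is summarised, a footnote separates no values, and a cohort-level note cannot describe rescue that varies by patient and over time within 0.5–1 mg.

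**Individual data remain visible.** SAP IX.C plans overlay plots and by-patient listings, and SAP IX.G lists concomitant medication. With seven low-dose patients a careful reader could reconstruct the picture. This limits the harm but does not correct the summary table.

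**No decision rests on these means.** The study is descriptive, so no error rate or power is affected. Escalation uses dose-limiting toxicities and committee review, and the beta-CTX discontinuation rule uses individual values. This is correct. The issue is how the dose-response is reported.

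**Stronger readings a reader might infer are not supported.**
- *That Modules 2 and 3 are confounded too.* They are tabulated separately and denosumab is planned for every patient. The same holds within 1.5–3 mg of Module 1.
- *That the table simply displays the denosumab effect.* The low-dose columns contain values without denosumab as well as values after rescue, so the two effects are inseparable rather than one replacing the other.
- *That rescued patients fell far below baseline.* Protocol 1.2.5 speaks of normalisation, and in another drug's trial.
- *That setting values below quantification to zero distorts the result.* The documents give no quantification limit and no such value.

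**Conclusion.** The concern holds for Module 1, across the 1 to 1.5 mg step. The planned dose columns and the pooled column cannot separate RXC004 from denosumab, and the apparent dose effect can be absent or inverse. Under the step 3 assumptions the low-dose mean before rescue is +125 to +225 pg/mL for a 350 pg/mL rise, or 0 to +100 for a 100 pg/mL rise, against zero or less for the 17 prophylaxed patients. After rescue it is −50 to +50.

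This rests on reading the reported at-or-below-baseline levels as applying to individual patients, and on the six patients in the protocol's count being drawn from the seven at 0.5–1 mg. Reversal is possible, not established. Within 1.5–3 mg, and in Modules 2 and 3, the limitation is masking: an RXC004 effect on beta-CTX may be hidden, but denosumab policy does not differ between the groups compared. The change is worth making because it is cheap and concerns the main tabulated bone marker.

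**What to change.** For Module 1, add a beta-CTX presentation by denosumab status:

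1. **0.5 and 1 mg, before denosumab.** For each patient, give the maximum change from baseline before the first denosumab dose. For each cohort, give the proportion reaching the +350 or 1,000 pg/mL trigger, counting every patient in the cohort. Do not use by-visit means cut off at denosumab: they drop patients because their beta-CTX rose and leave the non-risers at later visits.
2. **0.5 and 1 mg, after denosumab.** Show these values separately.
3. **1.5–3 mg.** Label the columns *RXC004 plus prophylactic denosumab*.
4. **Overall column.** Omit it from this table.
5. **Statement.** Say that a dose trend across 1 to 1.5 mg is not interpretable.

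The SAP introduction says the Module 1 database was locked before the Module 2 and 3 changes were made, so this would be a documented addition in the study report. Concomitant treatments are already recorded in the CRF (Protocol 2.3.1). The cost is one table re-run and very small cells (4 and 3 patients before any split). Changing how values below quantification are imputed is optional and not part of this point.

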#### **L. Other Assessments**

DXA scan results, including change from baseline in BMD, concomitant radiotherapy, and concomitant transfusions will be presented in the data listings.

### **X. Pharmacokinetics Analyses**

Plasma concentration data will be listed and summarized descriptively by analyte, module, dose level and nominal time points.

Descriptive statistics will include the number of patients (n), mean, SD, coefficient of variation (CV%), median, minimum, and maximum. Concentration values below the limit of quantification (BLOQ) will be treated as 0 for the computation of descriptive statistics.

The detailed derivation for the pharmacokinetic parameters based on plasma concentration data will be described in a separate analysis plan. All reported PK parameters will be listed and summarized descriptively similar to the concentration data. Geometric mean will also be presented for PK parameters such as AUC, Cmax and other parameters as appropriate and medians for Tmax. Plots of mean PK concentrations will be done with a different line and color for each dose level. Individual subject concentration data will be plotted with separate plots for each dose level.
